10.4 Determination of sample size

Part 1 (CHICO)

This study uses historical controls estimated from cure rates presented in two publications [15][16]. The historical cure rates are as follows.

Publication	Age range	Sero-conversion rate (95%CI) in placebo patients
Andrade et al 1996	7-12	3/65 = 5% (1%,13%)
Sosa et al 1998	6 -12	2/44= 5% (1%,16%)

For the primary objective, superiority over placebo will be confirmed if the lower limit of the 95% CI for the nifurtimox (60-day regimen) cure rate is greater than 16%, the larger of the upper limits of the 95% CIs from the two publications.¹⁹⁴

According to Guhl et al [32], nifurtimox 12 month post treatment cure rate is about 55%, with a sample size of 200 for the 60-day regimen, the power is 99% for the lower limit of the 95% CI to be greater than 16%.¹⁹⁵

The number of subjects in the 30-day treatment regimen is based on the width of a 95% CI for the difference of two proportions. A sample size of 100 subjects for the 30-day subjects together with 200 subjects for the 60-day subjects will produce a CI with a half-width of approximately 0.12.

Part 2 (CHICO SECURE)

¹⁹⁴ Modified as per amendment 2

¹⁹⁵ Modified as per amendment 2

	Integrated Clinical Study Protocol BAY A2502/16027
03 NOV 2020	Version 11.0

Page: 84 of 259

According to Sosa-Estani [15, 35], the 48 months post treatment cure rate for benznidazole is about 5% as confirmed by two types of assay. For the primary objective, assuming a drop-out rate of 15%, the expected number of patients to be observed at the end of Part 2 (i.e., 48 months post treatment) in the 60-day regimen would be 170 out of the 200 patients in Part 1. Using the assumptions of 170 nifurtimox 60-day regimen patients in Part 2, a 5% cure rate, and that seronegative conversion events follow Poisson distribution, the estimated incidence rate is calculated to be 1.32% and the 95% CI of the incidence rate is (0.61%, 1.51%).

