## 6.2.2 Part 2 (CHICO SECURE)

## 6.2.2.1 Primary efficacy variable and analysis

## Primary efficacy variable

The primary efficacy variable will be the incidence rate of seronegative conversion measured and confirmed by two types of assay (recombinant ELISA and IHA) in subjects who were randomized and received at least one dose of the 60-day nifurtimox treatment regimen. Both test results should be negative for the subject to be considered as seroconverted. Incidence rate is the number of new cases of seronegative conversion over the study period (i.e. 4 years after end of nifurtimox treatment) divided by the person-time at risk.

Subjects used antitrypanosomal drugs during the study before they were seroconverted will not be considered as sero-convertion, but their time of observation till when they took antitrypanosomal drugs will be factored into the person time calculation.

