#### Primary analysis of the primary efficacy variable

The difference in the incidence rate of nifurtimox subjects with seronegative conversion (60-day regimen) and the seronegative rate estimated from historical data will be tested using a Poisson two-sided 95% exact confidence interval (CI).

## BAY No. A2502/IMPACT No. 16027 Page: 23 of 30

The incidence rate of seronegative conversion for the primary efficacy variable will be modelled using a Poisson distribution with a 2-sided 95% exact CI. The rate will be estimated as the number of seronegative conversion divided by the total time at risk (person-year) during the study. The rate of seronegative conversion (R) and a 2-sided limits ( $R_l$ ,  $R_u$ ) of the 95% CI for the rate can be calculated using the following formula [4]

$$R = \frac{n}{\sum_{i} N_i * V_i}, i = 1, 2, ... K$$

$$R_{l} = \frac{\chi^{2}_{2n,\alpha/2}}{2\sum_{t} N_{t} * V_{t}}, i = 1, 2, ... K$$

$$R_{u} = \frac{\chi^{2}_{2(n+1),1-\alpha/2}}{2\sum_{i} N_{i} * V_{i}}, i = 1, 2, \dots K$$

where n is the number of seronegative conversion observed, N the total subjects at risk in annual visit *i*, Vi the *i*th annual visit, *K* the total number of visits,  $R_i$  and  $R_u$  are lower and upper confidence limits for the rate of seronegative conversion respectively,  $\chi^2_{\nu,a}$  is the chi-square quantile for upper tail probability on v degrees of freedom.

This study uses an external control group of untreated patients with Chagas' disease in the 4-year follow-up period presented in Sosa et al. [7, 7]. In the reference, seroconversion to a negative result in the placebo group after 4-year follow-up was detected in 2 subjects with conventional serology and in 0 subjects with IHA test. Thus, none of the subjects in the placebo group was considered as seroconverted by both test results. The person time at risk was on average 44 \* 4 = 176 person years. The incidence rate estimate was 0% (0 / 176).

Superiority will be confirmed if the lower limit of the CI for the incidence rate of seronegative conversion for subjects in 60-day regimen is greater than the rate of historical placebo subjects with sero-conversion (i.e. 0 %).

Frequency counts and percentages of seronegative conversion will be provided by visit.

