## Part 2 (CHICO SECURE)

According to Sosa-Estani [7, 7], the 48 months post treatment cure rate for benznidazole is about 5% as confirmed by two types of assay. For the primary objective, assuming a drop-out rate of 15%, the expected number of patients to be observed at the end of Part 2 (i.e. 48 months post treatment) in the 60-day regimen would be 170 out of the 200 patients in Part 1. Using the assumptions of 170 nifurtimox 60-day regimen patients in Part 2, a 5% cure rate, and that seronegative conversion events follow Poisson distribution, the estimated incidence rate is calculated to be 1.32% and the 95% CI of the incidence rate is (0.61%, 1.51%).

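### The Part 2 planning confidence interval has a wrong upper limit (1.51% printed, about 2.51% by the plan's own method), and the SAP's quantile definition inverts the limits if taken literally

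*Protocol*

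**What the plan says.** Protocol 10.4 (Part 2) plans for the 60-day regimen by "assuming a drop-out rate of 15"%, which takes the 200 patients of Part 1 to 170. With a 5% cure rate and Poisson events it concludes that "the estimated incidence rate is calculated to be 1.32% and the 95% CI of the incidence rate is (0.61%, 1.51"%). SAP 6.5 gives the same result: "the 95% CI of the incidence rate is (0.61%, 1.51"%).

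The method is a two-sided 95% exact Poisson interval (protocol 10.3.2.2, SAP 6.2.2.1). The rate is the number of conversions "divided by the total time at risk (person-year) during the study". For the external control, person-time is patients multiplied by four years: "The person time at risk was on average 44 \* 4 = 176 person years".

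In SAP 6.2.2.1 the lower limit R_l uses a chi-square quantile on 2n degrees of freedom with subscript α/2. The upper limit R_u uses one on 2(n+1) degrees of freedom with subscript 1−α/2. The legend says the symbol "is the chi-square quantile for upper tail probability on v degrees of freedom". Protocol 10.3.2.2 has the same legend, but its formula symbols are not legible in the text available for review.

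The decision rule uses one limit only: "Superiority will be confirmed if the lower limit of the CI for the incidence rate" exceeds the historical placebo rate, taken as 0%.

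**The concern.** The printed interval has the wrong shape. Its lower arm is 1.32 − 0.61 = 0.71 points and its upper arm is 1.51 − 1.32 = 0.19 points. An exact Poisson interval is right-skewed, so its upper arm should be the longer one whatever the inputs.

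This is the only precision statement for the Part 2 primary endpoint, and it stands in both governing documents. A reader would take the rate to be known about twice as precisely as the design can deliver.

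The tail definition matters for a different reason: it governs the interval that will be reported. The same method is reused for the 30-day regimen, the age categories and non-conventional serology. A programmer who follows the legend would produce a lower limit above the upper limit.

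**Working it through.** **Inputs**

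- Patients: 200 × (1 − 0.15) = 170 (protocol 10.4, SAP 6.5).
- Follow-up: 4 years from end of treatment (protocol 10.3.1.2, SAP 6.2.2.1).
- Person-years, inferred: T = 170 × 4 = 680, the same convention as the control's 44 × 4 = 176.
- Events, inferred: 170 × 0.05 = 8.5, rounded up to n = 9.
- α = 0.05, two-sided.

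**Are the inferred inputs the right ones?** The ratio of lower limit to rate depends only on n. Allowing for rounding, the printed figures put it between 0.605/1.325 = 0.457 and 0.615/1.315 = 0.468. The exact ratio is 0.432 for n = 8, 0.457 for n = 9 and 0.480 for n = 10, so only 9 fits. With n = 9, the printed rate and lower limit together need about 679.2 to 680.2 person-years, which agrees with 680.

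**Reproducing the printed figures** (subscripts read as lower-tail probabilities)

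- Rate: 9/680 = 1.3235%. Printed 1.32%; agrees.
- Lower limit: χ²(0.025; 18)/(2 × 680) = 8.2307/1360 = 0.6052%. Printed 0.61%; agrees.
- Upper limit: χ²(0.975; 20)/(2 × 680) = 34.1696/1360 = 2.5125%. Printed 1.51%; does not agree.

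Width: 2.51 − 0.61 = 1.91 points before rounding of the limits (2.5125 − 0.6052 = 1.9073), against 1.51 − 0.61 = 0.90 as printed.

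**Sensitivity to the inferred inputs**

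| Events | Person-years | Rate | Exact 95% CI |
|---|---|---|---|
| 8 | 680 | 1.18% | (0.51%, 2.32%) |
| 8.5 | 680 | 1.25% | (0.56%, 2.42%) |
| 9 | 680 | 1.32% | (0.61%, 2.51%) |
| 9 | 740 | 1.22% | (0.56%, 2.31%) |

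The 740 row assumes that each of the 30 drop-outs contributes 2 years.

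**Other methods at 9/680.** The upper limits are 2.19% (Wald), 2.51% (Byar), 2.52% (score) and 2.54% (log). None is near 1.51%.

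**What 1.51% would need.** With 9 events: 34.1696/(2 × 0.0151) ≈ 1,131 person-years, where the rate would be 9/1131 = 0.80%. A search over 1 to 79 events and 100 to 6,000 person-years found both printed limits together only at 21 events in about 2,119 to 2,132 person-years. The rate there is about 0.99%, which contradicts the printed 1.32%.

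**Tail definition, taken literally** (n = 9, T = 680)

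- R_l: the quantile with upper-tail probability 0.025 on 18 df is 31.5264, giving 31.5264/1360 = 2.32%.
- R_u: the quantile with upper-tail probability 0.975 on 20 df is 9.5908, giving 9.5908/1360 = 0.71%.

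The limits are inverted. Exchanging the two outputs does not recover (0.61%, 2.51%), because each limit keeps its own degrees of freedom. The printed 0.61% matches the lower-tail reading, so the formula is sound and the legend is wrong.

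**The case against.** The best counter-argument is that nothing turns on this. The superiority rule uses the lower limit, which is printed correctly. The figure of 170 comes from 200 less 15%. The planning upper limit will be superseded by the observed interval. The tail wording does not threaten the decision either: with one or more events, R_l exceeds zero under both readings, and inverted limits would be conspicuous in any output. All of that stands and limits the weight of the point.

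It is also fair that 9 events and 680 person-years are not printed. Rounding 8.5 up to 9 implies a cure rate of 9/170 = 5.3%, and 680 gives drop-outs no person-time although the analysis includes it. This moves the correct upper limit between about 2.3% and 2.5%. It does not bring it near 1.51%.

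A one-digit typing error is a natural explanation, but not the only one. Using n+1 = 10 degrees of freedom in place of 2(n+1) = 20 gives χ²(0.975; 10)/1360 = 20.483/1360 = 1.506%, which rounds to the printed figure. Which slip occurred cannot be settled from the documents. The possibility is a reason to check the planning calculation as well as the text; it does not defend the number.

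**Conclusion.** The concern holds on both counts.

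- **Planning interval.** The upper limit in protocol 10.4 and SAP 6.5 is wrong. With 9 events in 680 person-years it is 2.51%, one percentage point above the printed figure, and the printed width is less than half the correct one. The exact value rests on inferred inputs, but those are the ones that reproduce the other two printed figures, and every plausible alternative tried gives at least 2.3%.
- **Quantile definition.** The legend in SAP 6.2.2.1 contradicts its own formula and inverts the limits if programmed as written. Whether protocol 10.3.2.2 has the same fault depends on formula symbols that could not be read.

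The superiority decision, the planning lower limit and the sample size are unaffected. The errors should be corrected because they concern the only stated precision for the Part 2 primary endpoint and the definition of its reported interval.

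**What to change.** 1. In protocol 10.4 and SAP 6.5, restate the planning interval as 1.32% (0.61%, 2.51%) and print its inputs: 9 events, 680 person-years. If other inputs were used, print those and recompute all three figures.
2. In SAP 6.2.2.1, define the chi-square quantile by lower-tail (cumulative) probability. Alternatively, keep the upper-tail wording and exchange α/2 and 1−α/2 between the two formulas. Check protocol 10.3.2.2 and align it.
3. Confirm that the planning calculation and the analysis program use lower-tail quantiles, with 2n degrees of freedom for the lower limit and 2(n+1) for the upper.

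The cost is a text correction in two documents and a short program check. Sample size, data collection and the decision rule do not change. The stated precision becomes less favourable.

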10.5 Planned interim analyses

No interim analysis is planned for the entire study.

11. Data handling and quality assurance

In general, the criteria, rules, and procedures in this section apply to part 1 and part 2 of the study. Criteria, rules, and procedures not applicable to either part of the study are otherwise marked.

11.1 Data recording

The data collection tool for this study will be a validated electronic data capture system. Subject data necessary for analysis and reporting will be entered/transmitted into a validated database or data system (SAS).

Source documentation

It is the expectation of the sponsor that key data entered into the eCRF is supported by source documentation available at the site.

Study-specific data not needed for the subject's routine medical care (e.g., scores or questionnaires) may be entered directly into the eCRF, without availability of corresponding source documentation.

The site must implement processes to ensure availability of all required source documentation. A source document checklist (not part of this protocol) will be used at the site to identify the source data for key data points collected and the monitor will work with the site to complete this.

ECG tracings will be maintained with the subject's source documentation, and ECG findings will be entered into the eCRF.

Completed subject diaries will be collected by site personnel at specific study visits (see Table 9–1). Information entered onto the subject diaries will be used to assess drug accountability and treatment compliance, and entered into the eCRF. The completed diaries will be maintained with the subject's source documentation.¹⁹⁶ (Not applicable to part 2)

¹⁹⁶ Text added to describe that subject diaries will be considered as source documentation for this study (Amendment 1)

	Integrated Clinical Study Protocol BAY A2502/ 16027
03 NOV 2020	Version 11.0

On the days of PK blood sampling, the investigator should document if the patient was on stable dose (stable dose = last 6 doses taken). The actual sampling date and sampling time should be documented. Failure to comply with the documented sampling windows or missing samples does not invalidate the subject or the sample for the PK evaluation. (Not applicable to part 2)

Page: 85 of 259

For subjects consenting to undergo PK blood sampling, blood samples will be sent to the sponsor, and the following data will be entered into the SAS after database lock for part 1 of the study.

Administered dose and exact times of two medication intakes during the visit, exact times of blood sampling, time of first dose after blood sampling, and samples collected within time window will be recorded in the eCRF.¹⁹⁷ (Not applicable to part 2)

Data recorded from screening failures

Data of 'only screened subjects' will be recorded at least as source data, as far as the reason for the premature discontinuation is identifiable. In addition to the applicable inclusion and/or exclusion criteria, the following data should be recorded in the eCRF:

- Demographic information (subject number; year of birth/age; sex; if applicable race/ethnicity)
- Date of informed consent
- Reason for premature discontinuation
- Date of last visit

These data will be transferred to the respective database.

For screening failures with an SAE, the following data should be collected in the eCRF in addition to the data specified above:

- All information related to the SAE such as:
 - Concomitant medication
 - o Medical history
 - Other information needed for SAE complementary page

11.2 Monitoring

In accordance with applicable regulations, GCP, and sponsor's/CRO's procedures, monitors will contact the site prior to the start of the study to review with the site staff the protocol, study requirements, and their responsibilities to satisfy regulatory, ethical, and sponsor's requirements. When reviewing data collection procedures, the discussion will also include identification and documentation of source data items.

¹⁹⁷ Modified as per amendment 2

	Integrated Clinical Study Protocol
	BAY A2502/ 16027
03 NOV 2020	Version 11.0

The sponsor/designee will monitor the site activity to verify that the:

- Data are authentic, accurate, and complete. Supporting data may be requested (example: blood glucose readings to support a diagnosis of diabetes).
- Safety and rights of subjects are being protected
- Study is conducted in accordance with the currently approved protocol (including study treatment being used in accordance with the protocol)
- Any other study agreements, GCP, and all applicable regulatory requirements are met.

The investigator and the head of the medical institution (where applicable) agrees to allow the monitor direct access to all relevant documents.

11.3 Data processing

Data will be collected as described in Section 11.1. Clinical data management will be performed in accordance with applicable sponsor's/CRO's standards and data cleaning procedures. This is applicable for data recorded on eCRF as well as for data from other sources (e.g., IVRS/IWRS, laboratory, ECG, ePRO, adjudication committees).

For data coding (AEs, medication), The Medical Dictionary for Regulatory Activities will be used for AEs, and the WHO Drug Dictionary will be used for prior and concomitant medications.¹⁹⁸

After its initial release for biometrical analysis, the clinical database is planned to be re-opened for the inclusion of the PK data.¹⁹⁹ (Not applicable to part 2)

11.4 Missing data

In general, no imputations will be made for missing data other than those described in Section 10^{200} More details will be provided in the SAP.

11.5 Audit and inspection

To ensure compliance with GCP and regulatory requirements, a member of the sponsor's (or a designated CRO's) quality assurance unit may arrange to conduct an audit to assess the performance of the study at the study site and of the study documents originating there. The investigator/institution will be informed of the audit outcome.

In addition, inspections by regulatory health authority representatives and IEC(s)/IRB(s) are possible. The investigator should notify the sponsor immediately of any such inspection.

The investigator/institution agrees to allow the auditor or inspector direct access to all relevant documents and allocate his/her time and the time of his/her staff to the auditor/inspector to

¹⁹⁸ Text modified for clarity (Amendment 1)

¹⁹⁹ Text deleted for clarity (Amendment 1)

²⁰⁰ Text added for clarity (Amendment 1)

	Integrated Clinical Study Protocol	
	BAY A2502/ 16027	
03 NOV 2020	Version 11.0	Page: 87 of 259

discuss findings and any issues. Audits and inspections may occur at any time during or after completion of the study.

11.6 Archiving

Essential documents shall be archived safely and securely in such a way that ensures that they are readily available upon authorities' request.

Patient (hospital) files will be archived according to local regulations and in accordance with the maximum period of time permitted by the hospital, institution, or private practice. Where the archiving procedures do not meet the minimum timelines required by the sponsor, alternative arrangements must be made to ensure the availability of the source documents for the required period.

The investigator/institution notifies the sponsor if the archival arrangements change (e.g., relocation or transfer of ownership).

The investigator site file is not to be destroyed without the sponsor's approval.

The contract with the investigator/institution will contain all regulations relevant for the study center.

12. Premature termination of the study

All criteria, rules, and procedures in this section apply to part 1 and part 2 of the study.

The sponsor has the right to close this study (or, if applicable, individual segments thereof [e.g., treatment arms; dose steps; centers]) at any time, which may be due but not limited to the following reasons:

- If risk-benefit ratio becomes unacceptable owing to, for example,
 - Safety findings from this study (e.g., SAEs)
 - Results of any interim analysis
 - Results of parallel clinical studies
 - Results of parallel animal studies
 (e.g., toxicity, teratogenicity, carcinogenicity or reproduction toxicity).
- If the study conduct (e.g., recruitment rate; drop-out rate; data quality; protocol compliance) does not suggest a proper completion of the trial within a reasonable time frame.

The investigator has the right to close his/her center at any time.

For any of the above closures, the following applies:

- Closures should occur only after consultation between involved parties. Final decision on the closure must be in writing.
- All affected institutions (e.g., IEC(s)/IRB(s); competent authority(ies); study center; head of study center) must be informed as applicable according to local law.

Version 11.0

Page: 88 of 259

- All study materials (except documentation that has to remain stored at site) must be returned to the sponsor. The investigator will retain all other documents until notification is given by the sponsor for destruction.
- In the event of a partial study closure, ongoing subjects, including those in post study follow-up, must be taken care of in an ethical manner.

Details for individual subject's withdrawal can be found in Section 6.3.1.

13. Ethical and legal aspects

In general, the criteria, rules, and procedures in this section apply to part 1 and part 2 of the study. Criteria, rules, and procedures not applicable to either part of the study are otherwise marked.

13.1 Investigator(s) and other study personnel

This study will be conducted at investigational study centers in Latin America and Mexico.

The medical expert for this study is ^{PPD} [name].

The Study Manager and the Medical Expert will assign the coordinating investigator responsible for signing the clinical study report.

All other study personnel not included in this section are identified in a separate personnel list (not part of this clinical study protocol) as appropriate. This list will be updated as needed; an abbreviated version with personnel relevant for the centers will be available in each center's investigator site file.

Whenever the term 'investigator' is noted in the protocol text, it may refer to either the principal investigator at the site, or an appropriately qualified, trained and delegated individual of the investigational site.

The principal investigator of each center must sign the protocol signature page and must receive all required external approvals (e.g., health authority, ethics committee, sponsor) before subject recruitment may start at the respective center. Likewise, all amendments to the protocol must be signed by the principal investigator and must have received all required external approvals before coming into effect at the respective center.

A complete list of all participating centers and their investigators, as well as all required signature documents, will be maintained in the sponsor's study file.

The global sponsor of this study is identified on the title page of this protocol. If required by local law, local co-sponsors will be nominated; they will be identified on the respective country-specific signature pages.

External data evaluation bodies

An independent Data Monitoring Committee (DMC) will meet periodically to review the safety data of enrolled subjects, as well as the continuing scientific merit of the trial.

	Integrated Clinical Study Protocol BAY A2502/16027
03 NOV 2020	Version 11.0

Page: 89 of 259

The DMC may recommend stopping enrollment in the case of a negative risk/benefit assessment. The DMC will be comprised of a minimum of two clinicians with expertise in relevant clinical specialties and at least one statistician knowledgeable about statistical methods for clinical trials. Each committee member will be screened for evidence of an absence of serious conflicts of interest. The operation of the DMC will be governed by a charter that will describe the group's frequency of meetings, procedures (including, but not limited to, periodic safety monitoring), and requirements for reporting its observations to the Sponsor. (Not applicable to part 2)

